Official title: Dose-response of physical exercise on pelvic floor muscle function in postmenopausal women with urinary incontinence

Number: NCT04351750

Document date: 12/22/2021

Study protocol

Urinary incontinence (UI) symptoms are highly prevalent among women, and menopause may be a risk of developing urinary incontinence¹. During the menopausal transition, not only the hormonal secretion is changed but also the physical activity is affected. The time women spend in physical activity is reduced and the time spent in sedentary behavior is increased in postmenopausal women². Studies have shown that physical activity acts in a bidirectional manner, exerting either a preventive or an aggravating effect on urinary incontinence³. Individuals with sedentary lifestyle and insufficient physical activity (< 150 min/week) are at risk of developing UI, and regular physical activity exerts a protective effect in preventing UI, but the optimal type, duration, and intensity of exercise for the female older adult population remain unknown. In addition, objective measurements of pelvic floor muscle function was needed as the use of self-reported measures may cause response bias⁴. The aim of the study was to investigate the effect of different intensity of exercise on pelvic floor muscle function and health-related quality of life (HRQoL) in postmenopausal women with UI. We hypothesized that (a) both high- and low-intensity physical activities could improve pelvic floor muscle strength and HRQoL in postmenopausal women with UI, and (b) the improvement in high-intensity group would be higher than that in low-intensity group. A randomized trial was conducted to compare the effect of different exercise intensity on pelvic floor muscle function in postmenopausal women with UI (n=38). The participants were randomly allocated to high-intensity group, low-intensity group or control group. Each group received an 8-week intervention. Both high-intensity group and low-intensity group received a multimodal exercise program including aerobic exercise, resistance exercise, and pelvic floor muscle training. The control group underwent only pelvic floor muscle training. The outcome measures including pelvic floor muscle function, UI symptom severity, HRQoL,

voiding function, and physical activity levels were assessed at baseline and after 8-week intervention.

Statistical analysis plan

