Data analysis was performed by Statistical Product and Service Solutions (SPSS) version 22.0 (SPSS, Chicago, IL, USA). The descriptive data were presented as mean, standard deviation (SD), number and percentage. The one-way ANOVA tests were used to compare the continuous data between two groups and chi-square tests were used for categorical data. Shapiro-wilk tests were used to assess the normality of data. Paired-t tests and McNemar's test were used for within-group comparisons. The repeated-measure ANOVA tests and chi-square tests were used to compare changes in outcomes between groups after intervention; ANCOVA tests were used if adjustment for significant differences between groups on outcomes at baseline was needed. A significant level was set at p-value<0.05.

Reference

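### Categorical outcomes are compared between arms by chi-square on an undefined change, with no adjustment for baseline status and no adjusted method that would fit them

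*Combined protocol and SAP*

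**What the plan says.** The Statistical analysis plan treats categorical outcomes in three places.

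- Within arms: "Paired-t tests and McNemar's test were used for within-group comparisons". McNemar's test needs paired binary data, so the plan expects some binary outcomes recorded at both visits.
- Between arms: "The repeated-measure ANOVA tests and chi-square tests were used to compare changes in outcomes between groups after intervention". Chi-square is the only between-arm method that can apply to categorical outcomes. How a categorical change is coded is not stated.
- Adjustment: "ANCOVA tests were used if adjustment for significant differences between groups on outcomes at baseline was needed". This is the only baseline adjustment named, and it depends on a significant baseline difference.

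The Study protocol section gives 38 participants and three arms ("The participants were randomly allocated to high-intensity group, low-intensity group or control group") without an allocation ratio. It lists outcome domains measured at baseline and week 8 and does not say which are categorical. The threshold is p<0.05.

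**The concern.** Chi-square on a categorical change could mean two things. It could be a table of week-8 status by arm, which contains no baseline value. Or it could be a table of improved versus not improved, where baseline is used to code the outcome but is not adjusted for: a woman unaffected at baseline cannot improve, so an arm that starts with more affected women tends to show more improvers. Either way, a chance baseline gap carries into the between-arm result.

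ANCOVA cannot repair this, because it is a method for continuous outcomes. McNemar's test uses the pairing but does not compare arms. At stake is whether a categorical difference between arms in this one small trial reflects the exercise programme or the starting position, and whether precision that the baseline data could supply is given up.

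**Working it through.** The documents give no event rate, power or sample-size figure, so there is no stated figure to reproduce.

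**Inputs from the documents.** 38 women, three arms, two visits, alpha 0.05.

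**Assumptions.** Equal allocation, so 38/3 = 12.7, about 13 per arm. A two-arm comparison of 13 v 13, such as high v low intensity. 50% affected at baseline. No treatment effect. A proportion p1 of affected women, and p0 of unaffected women, are affected at week 8, with (p1, p0) = (0.75, 0.25), (0.80, 0.20) or (0.85, 0.15). The baseline to week-8 correlation is then p1 − p0 = 0.5, 0.6 or 0.7. Pearson chi-square without continuity correction.

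**1. Chance of an imbalance.** The SD of the baseline difference is √(2 × 0.5 × 0.5 / 13) = 0.196, or about 20 points. Summing the two binomial distributions, P(gap of 4 or more women) = 16.9% (13.2% if 30% or 70% are affected). The mean gap in those comparisons is 4.69 women, and 4.69/13 = 0.361.

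**2. Carry-over under each reading.** With no true effect:
- Week-8 status: expected difference = baseline gap × (p1 − p0).
- Improved or not: expected difference = baseline gap × (1 − p1).

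Rejection rates for chi-square were obtained by exact enumeration. Those for the Mantel-Haenszel test (no continuity correction) come from 400,000 simulated null trials. The rows below are for comparisons with a gap of 4 or more.

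| | 0.75 / 0.25 | 0.80 / 0.20 | 0.85 / 0.15 |
|---|---|---|---|
| Week-8 difference | 0.361 × 0.50 = 18.1 points | 0.361 × 0.60 = 21.7 | 0.361 × 0.70 = 25.3 |
| Chi-square rejects, week 8 | 17.1% | 21.3% | 26.3% |
| Stratified Mantel-Haenszel rejects | 4.3% | 3.9% | 3.8% |
| Improved-or-not difference | 0.361 × 0.25 = 9.0 points | 0.361 × 0.20 = 7.2 | 0.361 × 0.15 = 5.4 |
| Chi-square rejects, improved | 5.3% | 3.4% | 1.7% |

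**3. Over all randomisations.** The 13 v 13 chi-square on week-8 status rejects in 7.6%. The figure is the same when baseline does not predict week 8 at all, so the excess over 5% comes from the small-sample approximation and not from imbalance. In the 83% of comparisons with a smaller gap, it rejects in 5.6%, 4.8% and 3.7%. The three-arm chi-square (13/13/12) rejects in 4.9% to 5.1%.

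**4. Precision.** The SD of the unadjusted week-8 difference is 0.196. The SD of the baseline-adjusted difference is 0.174, 0.160 and 0.143, a reduction of 11%, 18% and 27%. The large-sample formula 0.196 × √(1 − (p1 − p0)²) gives 0.170, 0.157 and 0.140, in line with this.

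**5. Sensitivity to the assumed persistence.** With a gap of 4 or more, the week-8 chi-square rejects in 7.7% when baseline does not predict outcome (0.5/0.5), 13.6% at 0.7/0.3 and 32.4% at 0.9/0.1. On the improved-or-not reading the order reverses. With no baseline correlation, a gap of exactly 4 gives a false difference of 15.4 points and 9.4% rejection.

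**6. The plan's trigger.** Even if a significance trigger were extended to categorical outcomes, it would miss gaps of this size. For 8 v 4 affected of 13, chi-square = 26 × (8 × 9 − 4 × 5)² / (13 × 13 × 12 × 14) = 70,304 / 28,392 = 2.48, below the critical value of 3.84.

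**The case against.** The strongest reply has four parts.

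*The text says changes.* A reader might infer that the chi-square test ignores baseline altogether. The documents do not support that. The sentence speaks of comparing changes, and a test on change categories uses baseline in its coding. What stands is narrower: the compared variable is undefined, and neither reading adjusts for baseline.

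*Randomisation protects the comparison.* A reader might also infer that imbalance inflates the trial's false-positive rate. It does not. The 17% to 26% rates describe only the 17% of comparisons selected for a large gap. This part of the reply stands in full, but it leaves the conditional bias and the loss of precision.

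*The harm shrinks under the reading closer to the text.* This is true for the persistence values used: 5 to 9 points, and rejection of 2% to 5%. One could reach 22 points by letting 60% of affected women improve (0.361 × 0.60). That requires only 40% to stay affected, which is not the case behind the week-8 figures, so the two must not be quoted together.

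*No affected outcome is named.* This also stands. The size cannot be computed from the documents, and presence of UI cannot be imbalanced because every participant has UI at entry. Even so, the plan provides McNemar's test and chi-square for outcomes, so it expects categorical outcomes, and some may vary at baseline.

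**Conclusion.** The point holds in a limited form. The plan offers no between-arm analysis of categorical outcomes that adjusts for baseline status, and its one named adjustment does not fit such data. The consequence is conditional bias in an imbalanced trial and avoidable imprecision. It is not average bias or a raised overall type I error.

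The size rests on equal allocation, 50% baseline prevalence and the assumed persistence, none of which the documents give. On those assumptions about one two-arm comparison in six is materially imbalanced. The effect is substantial if week-8 status is compared and modest if improvement is compared. There is no precision gain if baseline does not predict week 8, and no imbalance problem for an outcome on which all women start alike. It is worth correcting because the baseline data are already collected and the better method is simple.

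**What to change.** Name each categorical outcome. For each binary outcome that varies at baseline, replace the between-arm chi-square with a comparison of week-8 status by a Mantel-Haenszel test stratified by that outcome's baseline status, in its exact version where strata are small. Use it always, not only after a significant baseline test. Report the baseline-adjusted risk difference with a 95% CI. Where a category is only a cut of a score, analyse the score itself with its baseline as covariate.

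No new data are needed. The document describes the analysis in the past tense, so the cost may be a short reanalysis as well as revised wording. Strata in which every woman has the same week-8 status contribute nothing, and exact stratified tests can be slightly conservative.

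### ANCOVA is used only when a baseline test is significant, so an expected 88 to 95% of continuous outcomes stay on change scores, which are usually less precise

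*Combined protocol and SAP*

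**What the plan says.** The section headed Statistical analysis plan sets a default and an exception for between-group comparisons. The default is: "The repeated-measure ANOVA tests and chi-square tests were used to compare changes in outcomes between groups after intervention". The exception is: "ANCOVA tests were used if adjustment for significant differences between groups on outcomes at baseline was needed". The only threshold given is "A significant level was set at p-value<0.05".

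The baseline test that would trigger the exception is not named. The nearest candidate is the sentence "The one-way ANOVA tests were used to compare the continuous data between two groups", which speaks of two groups although the trial has three.

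The Study protocol section supplies the design. There are 38 women, and "The participants were randomly allocated to high-intensity group, low-intensity group or control group". The outcome domains and times are given as "The outcome measures including pelvic floor muscle function, UI symptom severity, HRQoL", continuing with "voiding function, and physical activity levels were assessed at baseline and after 8-week intervention", so there is one value before and one after the intervention. Hypothesis (b) in the same section is that "the improvement in high-intensity group would be higher than that in low-intensity group".

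**The concern.** Under randomisation the null hypothesis of a baseline test is true by design. How often the test is significant therefore depends on the threshold and the number of tests, not on whether adjustment would help. What decides the benefit is the correlation between baseline and 8-week values and the ratio of their SDs, and the trigger looks at neither.

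Three consequences follow:

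- Most continuous outcomes are expected to be analysed without adjustment, usually with wider intervals and lower power than the data allow.
- Chance can put different outcomes of the same trial on different models.
- Where a sizeable imbalance misses significance, the change-score estimate is shifted in that particular trial.

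Categorical outcomes and the within-group tests are not affected.

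**Working it through.** **Inputs.** From the documents: N = 38, three randomised arms, two assessments, threshold 0.05. Assumed, because the documents do not give them: arms of 13/13/12, normal data, a common slope, the trigger applied outcome by outcome, rho from 0.3 to 0.9, and s = 8-week SD / baseline SD of 0.8, 1.0 or 1.2. Effects are in baseline SDs. The plan states no power or sample-size figure to reproduce. Powers and type I errors come from 300,000 simulated trials per setting.

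**1. The default is a change-score analysis.** With two time points, the group-by-time F equals the one-way ANOVA F on changes. In a simulated data set both were 0.0375.

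**2. How often the trigger fires.** One three-group F test at 0.05 fires in 5% of trials, so 95% of continuous outcomes stay unadjusted. Any of three pairwise t tests fires in 12.1 to 12.4% by simulation, so about 88% stay. Three independent tests would give 0.95³ = 85.7%, but pairwise tests share arms.

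**3. Precision.** The ratio of ANCOVA variance to change-score variance is

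(1 − rho²)s² / (1 + s² − 2·rho·s) × (1 + 1/33),

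where 33 = 38 − 3 − 2 gives the average cost of estimating the slope. Example, rho 0.5 and s = 1: 0.75/1 × 1.0303 = 0.77.

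| rho | s = 0.8 | s = 1.0 | s = 1.2 |
|---|---|---|---|
| 0.3 | 0.52 | 0.67 | 0.79 |
| 0.5 | 0.59 | 0.77 | 0.90 |
| 0.7 | 0.65 | 0.88 | 1.00 |
| 0.9 | 0.63 | 0.98 | 1.01 |

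The maximum is 1.03, reached where rho × s = 1.

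**4. Power of the three-group test of change**, with assumed true gains of +1, +0.5 and 0 SD (high, low, control). Each cell gives the plan's rule with a three-group trigger, then ANCOVA always.

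| rho | s = 0.8 | s = 1.0 | s = 1.2 |
|---|---|---|---|
| 0.3 | 51% vs 80% | 42% vs 59% | 35% vs 44% |
| 0.5 | 65% vs 87% | 56% vs 68% | 47% vs 52% |
| 0.7 | 86% vs 97% | 80% vs 85% | 69% vs 69% |
| 0.9 | both above 99% | both above 99% | both 99% |

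**5. High-minus-low contrast.** The plan names no contrast; hypothesis (b) motivates this one. For a true difference of 1 SD with equal SDs, power under the plan's rule (three-group to pairwise trigger) against ANCOVA is:

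- rho 0.3: 56.1 to 57.3% vs 72.6%
- rho 0.5: 70.4 to 71.2% vs 80.5%
- rho 0.7: 89.5 to 89.8% vs 92.7%
- rho 0.9: all above 99%

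The difference detectable with 80% power at rho 0.3, 0.5, 0.7 and 0.9 is 1.34, 1.13, 0.88 and 0.51 SD for change scores, and 1.10, 0.99, 0.82 and 0.50 SD for ANCOVA.

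**6. Type I error.** Over all these settings the plan's rule gives 3.1 to 5.0% for the three-group test and 3.6 to 5.0% for the contrast; ANCOVA gives 4.9 to 5.1%. The rule is conservative, not inflated.

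**7. Unflagged imbalance.** Given a baseline gap g between two arms, the expected 8-week difference is the effect plus rho·s·g. The change-score estimate subtracts g, so it is shifted by −(1 − rho·s)·g. A high-low gap above 0.5 SD goes unflagged in 17% of trials (three-group trigger, mean gap 0.65 SD) or 13% (pairwise trigger, mean 0.62 SD). With equal SDs and the three-group trigger, the size of the mean shift in those trials is 0.45, 0.32, 0.19 and 0.06 SD at the four values of rho. Over all trials the mean error is within 0.004 SD of zero.

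**8. Mixed models in one trial.** Assume five continuous outcomes, one per listed domain. If they are independent, 1 − 0.95⁵ − 0.05⁵ = 22.6% of trials would use both models with the three-group trigger. At a 12.25% trigger rate the same formula gives 48.0%. With between-outcome correlation up to 0.7, the ranges are 15 to 23% and 32 to 48%.

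**The case against.** The strongest reply is that nothing here is invalid. Type I error is controlled, the estimate is unbiased on average, and the loss depends on quantities the documents do not give. With a rising SD and high rho it vanishes. All of that stands, and it makes this an efficiency point only. Not knowing rho still favours ANCOVA, because its average cost is small whatever rho and s are.

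The 1 SD high-low difference in step 5 is a generous choice. Under the gains assumed in step 4, that difference is 0.5 SD. With equal SDs the power is then 18% vs 25%, 24% vs 29%, 36% vs 40% and 79% vs 80% at the four values of rho. The gain is smaller, and at rho 0.3 to 0.7 neither analysis is adequately powered for this contrast. That qualification stands.

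The 3% ceiling is an average over randomisations. In a single trial the variance inflation of the ANCOVA contrast depends on the realised baseline gap and reaches 1.12 at the 95th percentile. This does not reverse the average preference for ANCOVA.

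The plan does not say that the trigger works outcome by outcome, and its reference to two groups may be a slip. If so, the three-group figure of 95% applies. The plan's condition that adjustment be needed may also leave discretion, but undefined discretion after baseline data are seen weakens pre-specification further.

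**Conclusion.** The concern holds. For continuous outcomes the plan lets a baseline significance test choose the model, and an expected 88 to 95% of outcomes stay on change scores. These are expectations; the realised share in one trial can differ.

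The cost is precision, not validity. It is large at low to moderate rho with a stable or falling SD (variance ratio 0.52 to 0.77 at rho 0.3 to 0.5). It shrinks to about nil at rho 0.9 with equal SDs, or at rho 0.7 to 0.9 with an SD that rises by 20%. These sizes rest on the assumed arm sizes, normality, common slope, rho and SD ratio. The direction needs less: averaged over randomisations, ANCOVA can lose at most about 3% in variance and can gain close to half within the range examined. With 38 women in three arms the rule should be changed.

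**What to change.** Delete the conditional clause and replace it with:

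> For each continuous outcome, the 8-week value is analysed by ANCOVA with group (three levels) and the baseline value of the same outcome as covariate, whatever any baseline test shows.

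Report the adjusted high-minus-low difference with its 95% CI, since hypothesis (b) is that comparison. Dropping baseline significance tests from the descriptive table is optional.

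No new data are needed: baseline values are already collected and ANCOVA is already named in the plan. One residual degree of freedom is spent (35 to 34; critical t 2.030 to 2.032). If the analysis has not been run, this is a wording change.

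Both sections are written in the past tense, so it may have been run. In that case rerun it in SPSS, label it as a change from the plan, and show the result under the plan's rule beside it. This does not restore pre-specification.
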